8.4 Treatment of Overdose

Study drug overdose is any accidental or intentional use of study drug in an amount at least 2 times higher than the dose indicated per-protocol for a given subject. Study drug compliance (see [Section 6.4](#)) should be reviewed to detect potential instances of overdose (intentional or accidental).

The Sponsor must be immediately notified of any instances of overdose and a protocol deviation must be thoroughly documented and reported per local regulations. Any study drug overdose during the study should be recorded on the source document and eCRF. The excess quantity and duration of the overdose should be recorded.

In the event of overdose, the subject should be closely monitored for any potential AEs. All AEs associated with an overdose should be entered on the Adverse Event eCRF. If the associated AE fulfills serious criteria, the event should be reported to the Sponsor or designee within 24 hours of awareness of the event. Any AEs or SAEs associated with an overdose will be reported using the procedures detailed in [Appendix 12](#).

8.5 Pharmacokinetics

Blood samples will be collected for PK analysis of RPT193 at the visits and time points specified in the SoA.

The analysis of RPT193 in blood samples will be performed at [REDACTED] using (a) validated liquid chromatography-mass spectrometry/mass spectrometry method(s) (LC-MS/MS). The Bioanalytical Reports for the determinations will be included in the clinical study report (CSR). Exploratory analysis of RPT193 metabolites or related compounds in blood samples may be conducted at Sponsor laboratories.

At the time points defined in the SoA, blood samples will be taken for the analysis of RPT193 (and possibly for RPT193 metabolites or related compounds), in blood samples. The blood samples will be taken via an indwelling intravenous (IV) catheter or by direct venipuncture into K2 ethylenediaminetetraacetic acid [EDTA]-containing tubes.

The actual date and time of each blood sample collection will be recorded in the eCRF.

Details about the collection, processing, handling, storage, and shipping of PK samples will be provided in the laboratory manual.

PK variables will be the plasma concentrations of RPT193 and their PK parameters. A complete list of PK parameters will be provided in the SAP.

8.6 Pharmacodynamics

Blood samples will be collected for pharmacodynamic analysis of RPT193 at the visits and time points specified in the SoA. The pharmacodynamic analysis of RPT193 will include but may not be limited to the assessment of CCR4 occupancy by flow cytometry, measurement of serum cytokines/chemokines levels by immune-assay, and blood cell immunophenotyping by flow cytometry. Note: immunophenotyping will only be performed for subjects in the US and Canada; immunophenotyping will not be performed for subjects in Poland.

8.7 Pharmacogenomics

A blood sample for DNA isolation will be collected from subjects who have consented to participate in the genetic analysis component of the study. Participation is optional. Subjects who do not wish to participate in the genetic research may still participate in the study.

In the event of DNA extraction failure, a replacement genetic blood sample may be requested from the subject. Signed informed consent will be required to obtain a replacement sample unless it was included in the original consent.

Details on processes for collection and shipment and destruction of these samples can be found in the laboratory manual.

8.8 Biomarkers

Collection of samples for biomarker research is also part of this study. The following samples for biomarker research are required and will be collected from all subjects in this study as specified in the SoA:

- Whole blood
- Serum
- Plasma
- Skin tape strips
- Skin swabs

Note: tape stripping is only required for subjects in the US and Canada; tape stripping should not be performed for subjects in Poland.

Samples may be stored for a maximum of 25 years (or according to local regulations) following the last subject's last visit for the study at a facility selected by the Sponsor to enable further analysis of biomarker responses to RPT193.

8.8.1 RNA Transcriptome Research

Subjects in the US and Canada will have skin tape stripping samples collected at the visits specified in the SoA; tape stripping should not be performed for subjects in Poland. Tape strips will be collected from lesional and non-lesional skin at baseline. Tape strip samples will also be collected at the subsequent visits specified in SoA at the same sites sampled at baseline. For each sampled site, 16 tape-strip units will be placed and removed from the exact same site one after the other. All skin sampling (microbiome samples, and tape strips) should be collected from adjacent sites within the same lesion, whenever possible. Details about the collection, processing, handling, storage, and shipping of tape strip samples will be provided in the laboratory manual and/or the Study Reference Manual.

Transcriptome studies will be conducted using whole transcriptome RNA sequencing, which facilitates the simultaneous measurement of the relative abundances of thousands of ribonucleic acid (RNA) species resulting in a transcriptome profile for each skin sample. This will enable the evaluation of changes in transcriptome profiles that may correlate with biological response relating to AD or the action of RPT193.

The same samples may also be used to confirm findings by application of alternative technologies.

8.8.2 Proteome Research

Plasma and serum proteome studies will be performed by immunoassay for specific proteins of interest. Multiplexed or individual immunoassays may be used to determine relative and/or quantitative changes in protein level because of treatment. Proprietary algorithms and standard statistical techniques, such as analysis of variance (ANOVA) and analysis of covariance (ANCOVA), may be used to identify individual proteins exhibiting statistically significantly different changes in their levels between samples and/or between groups of samples. Alternatively, differentially expressed proteins may be identified by mass spectrometry or equivalent technology. This will enable the evaluation of changes in proteome profiles that may correlate with biological response relating to disease and medically related conditions or the results of treatment. Details about the collection, processing, handling, storage, and shipping of plasma and serum samples will be provided in the laboratory manual.

The samples may also be used to confirm findings by application of alternative technologies.

8.8.3 Skin Microbiome Swab

All subjects will have collection of skin microbiome samples at the visits specified in the SoA. Skin microbiome sampling is a non-invasive procedure that involves passing a swab along the skin. Two skin microbiome samples will be collected at baseline, one from lesional and one non-lesional skin. A skin microbiome sample will also be collected at the subsequent visits specified in the SoA at the same lesional site sampled at Baseline.

All skin sampling (microbiome samples and tape strips) should be collected from adjacent sites within the same lesion, whenever possible.

Details about the collection, processing, handling, storage, and shipping of skin microbiome samples will be provided in the laboratory manual and/or the Study Reference Manual.

8.9 Other Study Procedures

8.9.1 Medical Photography

Medical photographs will be performed at selected sites at the visits specified in the SoA. One or more most affected body regions, per Investigator's judgment, may be photographed.

Photographs will be identified with the following information: study number, subject number, and visit name and date. Digital images will be uploaded [REDACTED] via the secure website for Sponsor review.

Details about the medical photography will be provided in the Study Reference Manual.

8.9.2 COVID-19-Related Considerations

COVID-19 Vaccination Guidance

Investigators and subjects should consider the schedule of their COVID-19 booster vaccine (if applicable) when planning the timing of their study participation. Where possible, the timing of vaccination should be planned so that a booster vaccination is not administered during the study treatment period. Ideally, administration of a COVID-19 booster vaccine (if applicable) should be given at least 4 weeks prior to the first dose of study treatment for live, attenuated vaccines and 2 weeks prior to the first dose of study treatment for mRNA vaccines. If unavoidable, vaccination with mRNA-based vaccines can proceed during the study, but every effort should be made to avoid administration during the final month of the treatment period, if possible. These events will not be considered major protocol deviations, but are considered prohibited therapies. It should be noted that the effect of RPT193 on the response to COVID-19 vaccination is unknown. The COVID-19 vaccine may lead to AEs (fever, chills, etc.), which will need to be captured and distinguished as related to the vaccine versus RPT193.

COVID-19 Testing Guidance

At the Screening visit (Visit 1) and Baseline visit (Visit 2) prior to the first dose of study treatment, all subjects must have a nasopharyngeal swab, or oropharyngeal swab, nasal swab, or saliva sample collected to test for the presence of the SARS-CoV-2 virus. The sample will be sent to the study's central laboratory or local laboratory, if necessary, for analysis by an acceptable diagnostic assay. Subjects with positive test results at Screening (Visit 1) will be considered screen failures and will not be allowed to enroll per the exclusion criteria for the study. Such screen failed subjects may be considered for rescreening at a later date following consultation with the study Medical Monitor. If results from the COVID-screening at the Baseline visit are immediately available and positive, the subject should be screen failed and may be considered for rescreening at a later date following consultation with the study Medical Monitor. If results from COVID-screening at the Baseline visit are not immediately available at the time of randomization, subjects are allowed to dose with study treatment at the Baseline visit

(Visit 2) provided the Screening test was negative and as long as there is no clinical suspicion of COVID-19 infection or subject recent exposure to an individual with a confirmed, active infection at the time of the Baseline visit.

If the subject's results are positive for SARS-CoV-2 following sample collection at Baseline (Visit 2), the subject will need to be notified immediately upon receipt of the results. The subject should be advised to begin self-isolation and self-monitoring procedures according to any applicable local, state, and/or country-specific health recommendations. Referral to an appropriate health care provider for management of the subject's COVID-19 diagnosis should also be made. The subject's COVID-19 diagnosis will be reported as medical history unless the subject's clinical course progresses such that criterion for SAE reporting is met (see [Appendix 12](#)), in which case, all applicable safety reporting procedures will be followed by the site. Sites will also have the option to perform an unscheduled test for the SARS-CoV-2 virus at any time during the treatment phase of the study should a subject's clinical presentation necessitate it, in the Investigator's opinion. The same notification and referral procedures, as outlined in the preceding paragraphs, should be followed by the site. However, it is expected that any COVID-19 diagnosis made from a sample collected after the initiation of study treatment administration be reported as an AE per the requirements of [Appendix 12](#) of this protocol. In the event that a subject tests positive for the SARS-CoV-2 virus at or after Baseline (Visit 2), the Investigator must consult with the study Medical Monitor to determine if the subject should continue with study drug treatment or discontinue from treatment. Determinations will be made on a case-by-case basis with the intent to minimize any increased risk for the subject.

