All safety analyses will be performed on the Safety Analysis Set. Adverse events will be coded using the Medical Dictionary for Regulatory Activities (MedDRA). Treatment-emergent adverse events (TEAEs) are defined as AEs that first occurred or worsened in severity after the first dose of study treatment. The AE summaries will be primarily based on TEAEs. Descriptive statistics for the number and percentage of subjects with TEAEs will be summarized by treatment arm, system organ class, and preferred term for all TEAEs, treatment-related TEAEs, serious TEAEs, and TEAEs leading to discontinuation of study treatment. All TEAEs will be further summarized by maximum severity and causality. All AEs will be present in a by-subject listing. Serious AEs, and TEAEs leading to discontinuation of study treatment will be present in separate listings.

No interim analysis for efficacy is planned.

Data Monitoring Committee:

There will be no independent Data Monitoring Committee for this study.

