8.3.1 Time Period and Frequency for Collecting AE and SAE Information

Adverse events and SAEs will be collected from the signing of the ICF until Follow-up /Visit 10 or 28 days after the last dose of study treatment if subject is terminated early.

All SAEs will be recorded and reported to the Sponsor or designee within 24 hours of the Investigator's awareness of the event, as indicated in [Appendix 12](#). The Investigator will submit any updated SAE data to the Sponsor within 24 hours of receipt of the information.

Investigators are not obligated to actively seek AE or SAE after conclusion of the study participation. However, if the Investigator learns of any SAE, including a death, at any time after a subject has been discharged from the study, and he/she considers the event to be reasonably related to the study treatment or study participation, the Investigator must promptly notify the Sponsor.

The method of recording, evaluating, and assessing causality of AE and SAE and the procedures for completing and transmitting SAE reports are provided in [Appendix 12](#).

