
 • Any abnormal laboratory test results (hematology, clinical chemistry, or urinalysis) or other safety assessments (e.g., ECG, radiological scans, vital signs measurements), including those that worsen from baseline, considered clinically significant in the medical and scientific judgment of the Investigator (i.e., not related to progression of underlying disease). • Exacerbation of a chronic or intermittent pre-existing condition including either an increase in frequency and/or intensity of the condition. • New conditions detected or diagnosed after study treatment administration even though it may have been present before the start of the study. • Signs, symptoms, or the clinical sequelae of a suspected drug-drug interaction. • Signs, symptoms, or the clinical sequelae of a suspected overdose of either study treatment or a concomitant medication. Overdose per se will not be reported as an AE/SAE unless it is an intentional overdose taken with possible suicidal/self-harming intent. Such overdoses should be reported regardless of sequelae. • "Lack of efficacy" or "failure of expected pharmacological action" per se will not be reported as an AE or SAE. Such instances will be captured in the efficacy assessments. However, the signs, symptoms, and/or clinical sequelae resulting from lack of efficacy will be reported as AE or SAE if they fulfil the definition of an AE or SAE.

Events NOT Meeting the AE Definition

 • Any clinically significant abnormal laboratory findings or other abnormal safety assessments which are associated with the underlying disease, unless judged by the Investigator to be more severe than expected for the subject's condition. • Because worsening of AD is captured by efficacy assessments, it will not be recorded as an AE, unless more severe than expected for the subject's condition. • Medical or surgical procedure (e.g., endoscopy, appendectomy): the condition that leads to the procedure is the AE. • Situations in which an untoward medical occurrence did not occur (social and/or convenience admission to a hospital). • Anticipated day-to-day fluctuations of pre-existing disease(s) or condition(s) present or detected at the start of the study that do not worsen.

Definition of TEAE

TEAE Definition

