
 A TEAE is any condition that was not present prior to treatment with the study product but appeared following treatment, was present at treatment initiation but worsened during treatment, or was present at treatment initiation but resolved and then reappeared while the individual was on treatment (regardless of the intensity of the AE when the treatment was initiated).

Definition of SAE

If an event is not an AE per definition above, then it cannot be an SAE even if serious conditions are met (e.g., hospitalization for signs/symptoms of the disease under study, death due to progression of disease).

An SAE is defined as any untoward medical occurrence that, at any dose:

a) Results in death

b) Is life-threatening
 
The term ‘life-threatening’ in the definition of “serious” refers to an event in which the subject was at risk of death at the time of the event. It does not refer to an event, which hypothetically might have caused death, if it were more severe.

c) Requires inpatient hospitalization or prolongation of existing hospitalization
 
In general, hospitalization signifies that the subject has been detained (usually involving at least an overnight stay) at the hospital or emergency ward for observation and/or treatment that would not have been appropriate in the physician’s office or outpatient setting. Complications that occur during hospitalization are AEs. If a complication prolongs hospitalization or fulfills any other serious criteria, the event is serious. When in doubt as to whether “hospitalization” occurred or was necessary, the AE should be considered serious.
 
Hospitalization for elective treatment of a pre-existing condition that did not worsen from baseline is not considered an AE.

d) Results in persistent or significant disability/incapacity
 
 The term disability means a substantial disruption of a person’s ability to conduct normal life functions. This definition is not intended to include experiences of relatively minor medical significance such as uncomplicated headache, nausea, vomiting, diarrhea, influenza, and accidental trauma (e.g., sprained ankle) which may interfere with or prevent everyday life functions but do not constitute a substantial disruption.

e) Is a congenital anomaly/birth defect

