## J. COVID-19 Pandemic Impacted Subjects Assessment

Subjects who are impacted by COVID will be excluded in the Per-protocol Set.

The number of subjects who missed visits due to COVID-19 and the impacts ("Quarantined", "Site temporarily closed", "Unable to commute to clinic", "Other") due to the missing visits will be summarized by treatment and overall, and a by-subject listing will be provided. Moreover, the number of subjects who have COVID-19 related TEAEs or COVID-19 related protocol deviations will be reported in the disposition table. Any major COVID-19 related protocol deviations will be summarized and listed.

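### A positive Baseline COVID-19 sample learned of after dosing is kept as medical history unless it turns serious, which conflicts with the protocol's own AE and TEAE definitions and may under-count non-serious events

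*Protocol*

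**What the plan says.** Protocol Section 8.9.2 requires a SARS-CoV-2 sample at Screening and again at Baseline before the first dose. A Baseline positive that is available at once makes the subject a screen failure. If the result is pending, "subjects are allowed to dose with study treatment at the Baseline visit", provided the Screening test was negative and there is no clinical suspicion or recent exposure. For a Baseline sample that then comes back positive, the "COVID-19 diagnosis will be reported as medical history unless the subject's clinical course progresses such that criterion for SAE reporting is met". The same section expects that "any COVID-19 diagnosis made from a sample collected after the initiation of study treatment administration be reported as an AE", with no condition on seriousness.

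Appendix 12 gives the general rules. Among the events that meet the AE definition it lists "New conditions detected or diagnosed after study treatment administration even though it may have been present before the start of the study". Its TEAE definition includes a condition that "was present at treatment initiation but worsened during treatment". Section 9.4.3 and SAP VII.B repeat that limb, and the Synopsis puts it as AEs that "first occurred or worsened in severity after the first dose of study treatment". None of the four sets a seriousness threshold. Under Section 8.3.1, "Adverse events and SAEs will be collected from the signing of the ICF until Follow-up".

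TEAE incidence is one of the two primary endpoints (Protocol Table 1). SAP VII.J also plans to report "the number of subjects who have COVID-19 related TEAEs".

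**The concern.** The general definitions and the COVID-19 rule give different answers for the same subject. Appendix 12 makes a diagnosis learned after dosing an AE, and makes worsening after first dose a TEAE whether or not it is serious. Section 8.9.2 offers one way out of medical history, which is to meet an SAE criterion. A site that follows 8.9.2 to the letter has no instruction to open an AE record for a mild or moderate illness that appears or progresses on study drug.

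At stake is the completeness of a primary safety endpoint. Any error runs in one direction, towards too few events. Worsening happens after randomization, so if it differed between active drug and placebo, the missing records would hide part of that difference.

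**Working it through.** The plan states no figure to reproduce, so the check compares texts, follows the record through the SAP, and then bounds the size.

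**1. Who falls under the rule.** Subjects with a negative Screening test, no clinical suspicion or recent exposure, a Baseline result pending at randomization, a first dose given, and then a positive result. Immediate positives are screen-failed, so in practice the medical-history sentence applies to subjects already dosed.

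**2. The rules side by side.**

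| Situation | Section 8.9.2 | Appendix 12 |
|---|---|---|
| Pre-dose sample, positive result learned after dosing | Medical history | AE (diagnosed after treatment, even if present earlier) |
| The same infection worsens after first dose, not serious | No route out of medical history stated | TEAE |
| The same infection meets an SAE criterion | Reported as SAE | SAE, and TEAE if it worsened on treatment |
| Sample taken after first dose | AE, any seriousness | AE |

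The list in Appendix 12 of events that are not AEs does not resolve this. It exempts worsening of AD, findings linked to the underlying disease, and day-to-day fluctuation of pre-existing conditions without worsening. An intercurrent infection that worsens is none of these. Appendix 12 also says that something outside the AE definition cannot be an SAE. The SAE exit in 8.9.2 therefore presupposes that a worsening course is AE-eligible, yet the section calls for a report only once it is serious.

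**3. What the SAP does with the record.** SAP VII.B identifies TEAEs by program from AE records with onset on or after the first dose (and within 30 days after end of treatment). SAP V.C tabulates medical history separately. No SAP step turns a medical-history entry into a TEAE, so a worsening left in medical history is absent from TEAE incidence and from the COVID-19 count in VII.J.

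**4. Illustration (invented case).** No symptoms on Day 1, positive result on Day 3, fever from Day 5 managed at home with no SAE criterion met. Under Appendix 12 this is a TEAE. Under a literal reading of 8.9.2 it stays in medical history. The same illness found from a swab taken the day after first dose is an AE under 8.9.2 itself.

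**5. Size.** Inputs: about 265 subjects (Protocol 9.2) or 268 (SAP III.C), with 67 per arm. The share of subjects dosed with a Baseline sample later found positive is not in the documents; 0.5% to 5% is assumed.

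- Low end: 265 × 0.005 = 1.3, about 1 subject in the trial.
- High end: 268 × 0.05 = 13.4, about 13 subjects in the trial.
- Per arm: 1.3/4 = 0.3 to 13.4/4 = 3.4.
- Effect of one missed subject on an arm's TEAE incidence: 1/67 = 1.5 percentage points at most, and zero if that subject has any other TEAE.

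The 1 to 13 are all assumed Baseline positives. Only those with non-serious onset or worsening after first dose can be missed.

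**The case against.** A fair defence has several parts.

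- **The sample precedes dosing.** An infection already present is not itself treatment-emergent, so separating pre-dose from post-dose samples is principled. This stands for an infection that does not worsen. It does not justify making seriousness the only exit.
- **The sentence governs the diagnosis.** It does not forbid separate AE entries for later symptoms or complications; a pneumonia first diagnosed on Day 5 could be entered as a new condition under Appendix 12. This also stands. A reader might infer that all non-serious COVID-19 events in these subjects are lost, but the text does not go that far. Capture is ambiguous, and loss is the literal worst case. Because 8.9.2 is silent, sites may differ.
- **Serious infection is still captured.** A reader might infer that the rule removes a named event of clinical interest. The list in Section 8.3.5 covers only infections that are serious or opportunistic, and Section 9.4.3 illustrates it with hospitalization, IV antibiotics and threat to life. The SAE exit largely keeps those.
- **Seriousness is not the top of a severity scale.** The medically-important criterion in Appendix 12 could bring some non-hospitalized courses in as SAEs, so it is too strong to say that every grade below severe is removed.
- **AE collection starts at consent.** This might suggest a further loss for infections caught during screening. A pre-treatment AE is not a TEAE, so the point does not bear on the endpoint.
- **The rule is the same in all blinded arms and touches few subjects.** True, and this limits how much the point matters.

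**Conclusion.** The inconsistency is real: Section 8.9.2 and Appendix 12 cannot both be followed for a Baseline positive learned of after dosing. The supportable conclusion is that non-serious COVID-19 onset or worsening after first dose may be missing from the AE data, or recorded differently across sites. TEAE incidence and the SAP's COVID-19 count could therefore be somewhat low.

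The numbers are small, at about 1 to 13 Baseline positives under the assumed 0.5% to 5%, with fewer who worsen without becoming serious. Efficacy analyses are not affected. The point merits correction because it touches a primary safety endpoint and costs little to repair, not because it is likely to change the safety conclusion.

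**What to change.** Change recording only; dosing and clinical management stay as they are.

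1. In Section 8.9.2, remove seriousness as the only exit from medical history and refer to Appendix 12.
2. State that a Baseline-sample infection that neither produces nor worsens symptoms after first dose is recorded with a pre-dose onset, as medical history or as a pre-treatment AE, and is not a TEAE. Choose one of the two and align the Appendix 12 bullet with it.
3. State that any symptom onset or worsening after first dose is entered as a separate AE record with its own onset date and severity, regardless of seriousness.
4. Check this against SAP VII.B, which works on onset date. An AE dated Day 1 would be flagged as a TEAE even without worsening, and SAP IV.D sets an onset known only to the month of first dose to the first-dose date. An AE with an earlier onset would miss later worsening unless a new record is opened. The eCRF guidance should therefore make pre-dose onset identifiable.

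The cost is a short edit to 8.9.2 and Appendix 12, a small change to eCRF guidance, a check of the SAP rule, and slightly higher TEAE counts.
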